Preliminary data demonstrating the systematic Development of Non-Invasive Brain Stimulation for Addiction.

Over the last 4 years our laboratories at the Medical University of South Carolina (MUSC) and Virginia Tech Carillion Research Institute (VTCRI) have performed 3 independent studies and 1 joint study which directly contribute to the rationale and design of the present proposal. While both of our research groups have a long history of publications which have contributed to the scientific thoughts that went into this proposal, the most germane studies are summarized below:

In Study 1, we demonstrated that the frontal-striatal circuits Figure 5. In a pilot study by [name] & [name], after 5 involved in limbic drive and in executive control can be differentially activated through TMS in healthy, nonsmokers. In this study TMS was applied to a cortical node of the limbic circuit (frontal pole/vmPFC) and to the executive control circuit (dlPFC) while participants were in the MRI environment [(10) Figure 3]. Thus, demonstrating that TMS can selectively modulate limbic regions.

days of vmPFC cTBS (Strategy 1), individuals that received real TMS had a significant decrease in mPFC, insula and cingulate response to cigarette cues. This was not present in the Sham group. (Data shown are within group contrasts Visit 1 vs Visit 6, Factorial design, k = 25, voxel level p<0.05, uncorrected).

In Study 2, we demonstrated that 6 sessions of LTD-like TMS (cTBS) to the vmPFC (Strategy 1 in the present proposal) delivered in a single day caused a specific decrease in orbitofrontal cortex and ventral

striatal/accumbens BOLD signal in cocaine users (all of whom smoked cigarettes) relative to sham stimulation ([name] et al 2015). At the time, this was the first study to apply multiple doses of cTBS to the vmPFC.

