The long term goal of the research is to develop non-invasive brain stimulation as an evidence-based tool to facilitate abstinence during the first week after a quit attempt, as this is a robust predictor of 6-month treatment outcomes with traditional pharmacotherapeutic and behavioral interventions. The next step in pursuit of that goal is to systematically and parametrically evaluate the efficacy of two promising TMS treatment strategies (LTP-like stimulation to the mPFC (Aim 1), LTP-like stimulation to the dIPFC (Aim 2)) as tools to change smoking behavior and brain reactivity to smoking cues. These aims will be addressed in serial (Aim 1 Years 1-3, Aim 2 Years 3-5). A randomized, double-blind, sham-controlled design will be used for each aim. In total, 138 smokers will be recruited from the tri-county area surrounding Winston-Salem, NC. Current cigarette smokers seeking to quit smoking and willing to set a quit date will be recruited from the tri-county area using digital and print advertising in diverse media outlets. Following informed consent and screening, participants will be randomized to receive real or sham TMS to the mPFC (Aim 1, Years 1-3) or the dlPFC (Aim 2, Years 3-5) (see Table 1 and TMS Procedures below for more details regarding sham controls and double blinding procedure). During the Treatment Phase, participants will receive 10 sequential days of TMS (with additional behavioral and MRI scanning (see Table 1). Participants will receive TMS at least 3 times a week for a total of 10 TMS sessions. During the follow-up phase, participants will receive 4 maintenance TMS sessions once a week for 4 weeks. During the Follow Up Phase, behavioral assessments will be acquired weekly for the first 4 weeks (see Table 2), and daily EMA will be acquired. Consistent with the CNDS model, the primary hypotheses are that LTP-like stimulation to the mPFC and LTP-like stimulation to the dlPFC will both lead to a decrease in

smoking cue-reactivity in the salience network (neuroimaging outcome), and cigarette value (behavioral outcome) but that directly targeting the value circuit (mPFC) will be more efficacious. Additionally, we will test the hypothesis that individuals with higher discounting rates and cigarette valuation at baseline will respond more to the stimulation strategies compared to those with lower baseline discounting and valuation (Exploratory Aim).

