Behavioral Outcomes: For the treatment phase (10 days of real/sham TBS), the primary behavioral outcomes include Cigarette demand (Q0 and alpha), Craving (QSU Intention, QSU Relief), and Delay Discounting (\$100 and \$1000). For the treatment phase the analysis will be performed using repeated measures ANOVA on change scores from baseline for each visit. The main independent variable in the ANOVA will be time (visits on day 1, 6, 10), group (real or sham) and their interaction. For correlations of observations across visits an AR(1) structure will be considered and compared with other structures such as compound symmetry and a general structure. The primary hypothesis is the interaction. If the interaction effect for an outcome is significant, we will conclude there is statistical evidence of overall treatment effect. If the spaghetti plots suggest trends (e.g., linear, quadratic, or piecewise changes) we will treat time as a continuous variable and fit repeated measures regression models along with group and its interaction with continuous time as independent variables.

Neuroimaging Outcomes: For the treatment phase, primary analysis. Image pre-processing will be conducted with FSL v. 5.0: (FMRIB Analysis Group, Oxford, UK) (108) realignment to the first volume, smoothing with an anisotropic 8-mm Gaussian kernel, high-pass filtering, resampling to 2-mm isotropic voxels, and stereotactic registration to the Montreal Neurological Institute 152-subject average template. Subjects with >3 mm movement (total mean frame displacement across the entire task) will be excluded from analysis.

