Hypothesis Aim 1: Based on the framework predicted by CNDS theory, and preliminary work (see Study 4), we anticipate that mPFC stimulation will lead to a decrease in brain reactivity to cues during the "allow" condition (passive limbic engagement). We will analyze the neuroimaging data in concert with the behavioral data, evaluating the hypotheses that 1) mPFC iTBS will decrease the brain reactivity to cues in the 'allow' condition (with no consistent link to the 'resist' condition) and that 2) this will be related to the behavioral change in a dose-dependent manner. This will be achieved by extracting the average BOLD signal timecourse and the percent signal change during the CIG versus NEU blocks from a priori anatomically defined regions of interest (ROIs), including the striatum (ventral striatum and dorsal striatum), insula, inferior frontal gyrus, and anterior cingulate cortex. Ventral striatal and dorsal striatal ROIs are derived from the FSL Oxford-GSK-Imanova striatal atlas, mapped via probabilistic diffusion tractography (109) in agreement with anatomical projection zones from the frontal cortex (1). Hypothesis Aim 2: Based on the framework predicted by CNDS theory, and prior studies of dlPFC stimulation in smokers (4-9), we anticipate that dIPFC stimulation will lead to an increase in executive control circuitry (left dlPFC, posterior parietal cortex) during the "resist" condition (executive engagement). As in Aim 1, we will analyze the neuroimaging data in concert with the behavioral data, evaluating the hypotheses that 1) dIPFC iTBS will decrease the brain reactivity to cues in the "resist" condition (with no consistent link to the "allow" condition) and that 2) this will be related to the behavioral change in a dose-dependent manner. The ROI based outcomes of Aim 2 will be compared with the outcomes of Aim 1 using standard general linear modeling as well as a data-driven hierarchical model (see Integration below). As an experimental control, for both Aims we will also calculate the percent signal change from the primary motor cortex, a region which should not be differentially modulated by mPFC or dIPFC stimulation. Although some studies have used the visual cortex as a control region a recent meta-analysis by our group demonstrated that the visual cortex is typically activated more to drug cues than neutral cues (78). Secondary functional connectivity analysis: Additionally, an exploratory seed-based functional connectivity analysis using psychophysiological interactions (PPIs) will be performed using the TMS stimulated ROIs (mPFC and dlPFC) and the striatal target regions (ventral striatum, dorsal striatum- defined above) as seed regions. These data will be compiled across participants and compared between the mPFC and dIPFC stimulation days. Group analyses will be performed using a random effects model limiting significant clusters to those that meet p<0.05 family-wise error corrected.

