
For the follow-up phase: We will test the hypotheses that behavioral change related to Strategy 1 and 2 will be based on an individual's baseline brain cue reactivity data. We will generate Kaplan-Meier curves of behavioral change for the four groups and compare these with cue-reactivity in the MPFC, insula, cingulate (salience network nodes) and striatum using log-rank tests and consider Cox's proportional hazards model to include covariates. Diagnostics will be performed to verify the assumptions such as homoscedasticity and normality. If it is merited, transformations on the outcomes will be considered. Linear contrasts will be utilized to test the hypothesis of equal effects in the two groups at any given time point. Covariates, such as gender and depression that were used to stratify, will be included.

Exploratory Aim: Evaluate baseline frontal striatal connectivity and discounting rate as factors to predict an individual's likelihood of responding to Strategy 1 versus Strategy 2. Finally, will compare the relative efficacy of Strategy 1 versus Strategy 2 on the behavioral change by constructing a computational model. We will test the hypotheses that individuals with a higher ratio of (mPFC-striatal)/(dlPFC-striatal) connectivity will be more likely to have a behavioral change after Strategy 1. Various demographics (e.g. gender, smoking history, socioeconomic status, subclinical depressive symptoms, self-efficacy, & motivation to quit will be evaluated as explanatory variables. This will be achieved by hierarchical linear modeling (HLM v. 7.0, Scientific Software International, Skokie, IL) of the behavioral variables of interest as well as the BOLD signal change in the striatum (caudate) between smoking and image blocks (e.g., CIG vs. NEU) in 'allow' and 'resist' (behavioral change variables nested within treatment (cTBS, iTBS)).

Analytical Plan

Primary data analysis will be done on the Intent to Treat sample (n=138; 69 per Aim: 46 active, 23 sham). Prior to formal statistical analysis, summary statistics for all variables will be obtained and spaghetti plots will be generated. All behavioral outcome measures will be based on standardized composite scores from the literature. We will also use data reduction techniques (such as factor analysis or principle component analysis) to confirm the applicability of the composite scores in our population. Analyses will be performed for each phase separately.

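### The primary imaging hypothesis concerns the salience network, but the primary imaging analysis names a different set of regions, without mPFC and without a composite, lead region or multiplicity rule.

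*Combined protocol and SAP*

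**What the plan says.** All references are to the combined protocol and SAP.

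- **Design.** The primary hypotheses are that mPFC and dlPFC stimulation both reduce "smoking cue-reactivity in the salience network (neuroimaging outcome), and cigarette value (behavioral outcome", with mPFC the more efficacious target.
- **Outcome Measure(s), follow-up phase.** This is the only place that says which regions are salience nodes: "cue-reactivity in the MPFC, insula, cingulate (salience network nodes) and striatum". Striatum stands outside the bracket.
- **Outcome Measure(s), treatment phase.** The section opens "Neuroimaging Outcomes: For the treatment phase, primary analysis". Under Hypothesis Aim 1, the measure is "percent signal change during the CIG versus NEU blocks from a priori anatomically defined regions of interest (ROIs", and the regions are listed as "including the striatum (ventral striatum and dorsal striatum), insula, inferior frontal gyrus, and anterior cingulate cortex".
- **Hypothesis Aim 2.** The regions named are left dlPFC and posterior parietal cortex, expected to increase under 'resist'. The numbered hypothesis that follows says dlPFC iTBS will decrease cue reactivity under 'resist' and names no region.
- **Objectives, Aim 2.** The neural response under 'resist' is expected to increase.
- **Preliminary data, Figure 5 legend.** In the pilot, "individuals that received real TMS had a significant decrease in mPFC, insula and cingulate response to cigarette cues".
- **Table 2** marks brain reactivity to smoking cues as a primary dependent measure, and the **Sample Size** section includes the brain measures in its power claim.

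**The concern.** A primary hypothesis needs a test that can confirm or refute it. For the behavioral outcomes the plan supplies one: the group-by-time interaction is declared the primary hypothesis. Imaging has no counterpart. The hypothesis is about a network, while the analysis is a set of separate regions that only partly overlaps that network. A striatal or inferior frontal change could be presented as primary success with insula, cingulate and mPFC unchanged. A change at the Aim 1 stimulation site would have no assured place in the primary analysis. In Aim 2, a rise or a fall under 'resist' could each be called the predicted result.

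The interim plan makes the timing matter. Data are analyzed at each 20% of recruitment, first at n=27, and the principal investigator receives unblinding codes for participants who have completed. A primary region left open could be settled after group-level data have been seen.

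**Working it through.** **1. Regions side by side.**

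| Region | Salience node in the follow-up text | Named in the Aim 1 primary list | In the Figure 5 pilot result |
|---|---|---|---|
| mPFC | yes | no | yes |
| Insula | yes | yes | yes |
| Cingulate | yes | yes (anterior) | yes |
| Ventral striatum | no (striatum listed apart) | yes | not in the legend |
| Dorsal striatum | no (striatum listed apart) | yes | not in the legend |
| Inferior frontal gyrus | no | yes | not in the legend |

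Two of the five named regions match a named node, three do not, and one of the three named nodes is missing. In the treatment-phase imaging text mPFC appears as a region only as a seed in the exploratory connectivity analysis. The pilot column needs care: Study 4 in the Preliminary data text, which describes the Figure 5 pilot, also reports striatum, and so does Significance 2.

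**2. Direction for dlPFC stimulation.**

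| Section | Region | Condition | Direction |
|---|---|---|---|
| Objectives, Aim 2 | not named | 'resist' | increase |
| Design | salience network | not named | decrease |
| Hypothesis Aim 2, opening | left dlPFC, posterior parietal | 'resist' | increase |
| Hypothesis Aim 2, item 1 | not named | 'resist' | decrease |

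An executive increase and a salience decrease could both be true. The rows that name no region cannot be assigned to either, so the conflict stays open.

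**3. Decision elements for imaging.** Given: the task contrast (CIG versus NEU), a condition per Aim ('allow' for Aim 1, 'resist' for Aim 2), two scans (Visits 1 and 10), and real and sham groups. Not given: which region or combination decides, the active-versus-sham change test, and error control across regions. The family-wise corrected cluster threshold follows the exploratory connectivity text and does not address the region tests. The Aim 1 versus Aim 2 comparison, needed for the claim that mPFC is more efficacious, names no region or condition.

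**4. Illustration of the open choice.** Assume that any of the five named regions counts at two-sided 5%. The plan states neither this rule nor the correlations.

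- Independent regions: 1 − (1 − 0.05)^5 = 1 − 0.95^5 = 0.226.
- Equally correlated regions: Z_j = √ρ·U + √(1−ρ)·E_j, and the quantity is P(max|Z_j| > 1.96) under the null. Results: 0.21 (ρ = 0.3), 0.18 (0.5), 0.15 (0.7), 0.13 (0.8).
- One pre-specified contrast: 0.05.

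**5. Why a single contrast rather than a correction over all five.** The plan states 28 per group for 80% power at d = 0.8. A two-sided two-sample t-test needs 26 per group (80.7% power), close to the stated figure; the plan's own calculation (4 time points, AR(1)) cannot be rerun because the correlation is not given. With 2:1 allocation and 78% retention, 138 × 0.78 ≈ 108, or 54 per Aim, 36 versus 18. For one region at d = 0.8, t-test power is 77.6% at 5% and 54.3% at 0.05/5 = 1%. Splitting alpha over the list would be expensive.

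**The case against.** Several points on the other side stand, and they limit what can be claimed.

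- A reader might infer that mPFC is excluded. It is not: the list is introduced as including certain regions, so it is open. mPFC is simply not named, and an open list fixes the deciding test even less.
- A reader might infer that striatum lacks pilot support, or that mPFC has the strongest. Neither is supported. Study 4 and Significance 2 report striatal effects, and the theory section makes striatum part of both target circuits. The Figure 5 legend lists mPFC, insula and cingulate without ranking, from uncorrected within-group contrasts after cTBS, whereas this trial uses iTBS. The point rests on the mismatch between sections, not on the pilot.
- The bracket naming salience nodes sits in a follow-up analysis of baseline reactivity and is not offered as a formal or exhaustive definition. It is, however, the only statement the plan makes.
- A reader might infer that Aim 2 has no salience analysis at all. The Aim 2 text says the data will be analyzed as in Aim 1, which plausibly carries insula and anterior cingulate over. mPFC would still be unnamed, and the direction conflict would remain.
- It would be too broad to say that no contrast exists. The task contrast, conditions, scan times and groups are given; the deciding region and the inferential test are not.
- The false-positive range measures unadjusted testing across regions. It would be the same for five regions that all matched the network.

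**Conclusion.** The mismatch holds. Following the plan as written tests something other than what the Design section declares primary, and nothing says which imaging result confirms or refutes that hypothesis. The size is best stated as overlap: two of five named regions match the plan's own nodes, and one of three nodes is unnamed. This takes the follow-up bracket as the plan's account of the network. For Aim 2 the sections also disagree on region and direction.

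The 13% to 23% range is an illustration that assumes an any-of-five rule at two-sided 5% and equal correlations between 0.8 and 0. It should not be read as the trial's actual type I error, since the plan commits to no such rule. The point should be settled before analysis; it does not undermine the design or the scanning.

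**What to change.** 1. Reconcile the Objectives, Design, Hypothesis Aim 1 and 2, and follow-up texts on region and direction. For Aim 2 the sponsor must do this first, because left dlPFC and posterior parietal cortex are the only regions tied to its stated mechanism.
2. Add mPFC to the treatment-phase region list.
3. Before any unblinded look, fix one primary imaging contrast per Aim: change from Visit 1 to Visit 10 in CIG-minus-NEU percent signal change, active versus sham, two-sided, in that Aim's named condition.
4. For the hypothesis as the Design section now states it, the default outcome is the average over mPFC, insula and cingulate. If the sponsor intends striatum (Aim 1) or the executive regions (Aim 2) to be primary, the Design section should say so.
5. Treat the remaining regions as secondary with Holm adjustment.

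The cost is plan wording and one more region mask, with no extra scanning. The downside is that an average can dilute an effect confined to one node; node-level results remain available as secondary.

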- 5. Is not at elevated risk of seizure (i.e., does not have a history of seizures, is not currently prescribed medications known to lower seizure threshold)

- 6. Does not have metal objects in the head/neck.
- 7. Does not have a history of traumatic brain injury, including a head injury that resulted in hospitalization, loss of consciousness for more than 10 minutes, or having ever been informed that they have an epidural, subdural, or subarachnoid hemorrhage.

8. Does not have a history of claustrophobia leading to significant clinical anxiety symptoms.

Exclusion Criteria

- 1. Any psychoactive illicit substance use (except marijuana, alcohol, and nicotine) within the last 30 days by self-report and urine drug screen. For marijuana, no use within the last seven days by verbal report and negative (or decreasing) urine THC levels. Participation will be discontinued if participants use psychoactive illicit substances (except nicotine and alcohol) after study initiation.
- 2. Meets DSM-V criteria for current axis I disorders of major depression, panic disorder, obsessivecompulsive disorder, post-traumatic stress syndrome, bipolar affective disorder, schizophrenia, dissociate disorders, eating disorders, and any other psychotic disorder or organic mental disorder.
- 3. Has current suicidal ideation or homicidal ideation.
- 4. Has the need for acute treatment with any psychoactive medication including anti-seizure medications and medications for ADHD.
- 5. Females of childbearing potential who are pregnant (by urine HCG), nursing, or who are not using a reliable form of birth control.
- 6. Has current charges pending for a violent crime (not including DUI related offenses).
- 7. Does not have a stable living situation.
- 8. Suffers from chronic migraines.
- 9. Does not have a stable phone number for contact through calling and/or texting.
- 10. Does not have a stable means of using WebEx (e.g. personal computer, Internet) for interaction with study personnel during COVID-19.

Sample Size

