Study Visit 1 (Behavior, MRI, TMS) will begin 1 week prior to the quit date. **Inclusion/Exclusion criteria:** To participate in the present study, participants must: 1) be 18-75 years of age, (2) smoke at least 10 cigarettes a day (on average; as measured by 1 month timeline follow-back (TLFB), (3) not have a history of or current psychiatric or neurologic disease, or traumatic brain injury (4) not be pregnant, , (5) not currently use psychoactive substances other than alcohol, nicotine, or marijuana; nor have current or recent (e.g. within the past 5 years) moderate/severe substance use disorder (DSM-V) (6) not have any barriers to making contact between the TMS coil and the skin (e.g. braids that cannot be removed), and 7) meet all criteria on a standardized MRI/TMS safety screen (TASS) (including but not limited to implanted electronic devices, bullets or metallic fragments, hair clips and piercings that cannot be removed). These inclusion/exclusion criteria are those used in Study 4 described in Preliminary Research. **Randomization.** Participants will be individually randomized and assigned to treatment or control conditions using stratified block randomization (with blocks of randomly varying sizes) prior to the study.

Experimental Procedure (Aim 1 and 2): Screening Visit – Consent. Participants will receive a series of assessments designed to evaluate nicotine dependence and use, psychiatric conditions, and mood. These include a standard clinical intake evaluation screen for research (used in other studies by the PI), MINI International Neuropsychiatric Interview (MINI 5 P) (88), Timeline Follow-Back (TLFB) (89), Beck Depression Inventory II (BDI) (90), State-Trait Anxiety Inventory (STAI) (91) and Profile of Mood States (POMS) (92). Data will be collected using REDCapTM, and entered directly into the online portal to ensure security and prevent data loss.

During COVID-19, study personnel will interact with participants via the Wake Forest Baptist Health (WFBH) institutional WebEx videoconference software as necessary. Participants will remotely sign and date the informed consent document.

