Study Visit Procedures: At all visits, individuals will provide a urine screen to detect recent use of drugs of abuse and pregnancy, a breath carbon monoxide (CO) sample to detect recent cigarette smoking, and a breath sample to test for recent alcohol use. During the consent visit, visits 1, 6, 10 and follow up visits samples will be collected to determine cotinine (nicotine metabolites) levels in the urine. Samples will be taken from the urine sample provided for the drugs of abuse screen, no additional samples will be required from the participant. At visits 1, 6, 10 and follow up visits (Assessment visits), participants will complete a battery of behavioral assessments following active TMS or sham (see Table 2). MRI scanning (at visits 1 and 10) will occur prior to TMS in order to isolate cumulative, rather than acute, effects of TMS. At all visits participants will be required to provide a CO reading at least 50% of their baseline CO measure to ensure they are at least 6 hours deprived from cigarettes. Cigarette deprivation will be use to increase craving and responding for cigarettes. Short term cigarette deprivation has known amplification effects on the brain response to smoking cues (93, 94). Moreover, we have extensive experience with successfully using this deprivation procedure (33, 41).

Table 2 1. Biochemical and self-report assessment of tobacco use and dependence						
Measure	Time (Min.)	Visits	Description			
Carbon monoxide (CO Level)	1	1-10, and follow-ups	Breath CO provides an accurate measure of recent exposure to CO , including from smoking combustible tobacco products (95). The CO measurement will be used to determine recency of smoking.			
Timeline Follow-Back (TLFB) interview	5	1, 6, 10, and follow-ups	This self-reported tobacco product use interview asks participants to retrospectively estimate the number of tobacco products they've used each day for the past 30 days or since the previous assessment, whichever is fewer (89).			
Fagerström (FTND)	3	1, 6, 10, and follow-ups	This 6-item questionnaire quickly assesses degree of cigarette dependence (96, 97). Test for Cigarette Dependence.			
2. Measures of t	tobacco pr	oduct value an	d sensitivity (**PRIMARY DEPENDENT MEASURES)			

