After the MRI scanning visits participants will be escorted into the Brain Stimulation Research Laboratory ([name] research suite) where scalp localization will be performed for the TMS procedure. The Cartesian position of the coil (X,Y,Z) will be determined by standardized positions from the EEG 10-20 system: 1) AFZ will be used for the mPFC stimulation (Aim 1), 2) F3 will be used for the left dlPFC stimulation (Aim 2). The angular position of the coil (pitch, yaw, roll) will be determined by the individual's cortical geography using the individual's T1 scan for guidance. The locations and coil orientation will be indicated on a nylon cap which will be worn during the TMS sessions. We will then determine the participant's resting motor threshold (RMT, the minimal amount of stimulation required over the hand area of the primary motor cortex to induce contraction of the APB muscle of the hand 50% of the time) via the standardized PEST procedure (106, 107). The procedures for acquiring the motor threshold, performing cortical localization, standardized procedures, blinding, establishing standardized paradigms and training regimens for all staff, as well as safety and ring the experimental procedures are consistent with our prior publications (7,27, 54, 63, 69, 78, 111). We will also publish a Standard Operating Procedure document and video file as supplementary material with any publications that arise from this project (as in 111, supplement).

For Aim1 (Strategy 1) stimulation will be over mPFC. For Aim 2 (Strategy 2) stimulation will be over the left dlPFC. The Aims will be pursued in serial, with a 2:1 active versus sham randomization for each Aim. Participants will receive 20 trains of stimulation (1200 pulses total; each train: 3 pulse bursts presented at 5Hz, 15 pulses/sec for 2 sec, 8 sec rest, 10 pulses/train; 110% RMT, MagPro) using a figure 8 coil (Coil Cool-B65 A/P). This is the iTBS sequence initially published (3) which has been used in clinical depression treatment (46). During each real and sham TBS session each day the amplifier output will be escalated ("ramping" in 5% increments over 30 seconds) up to 80% to 110% RMT to enhance tolerability. The time between the end of the TBS procedures and the beginning of the behavioral assessments will be compiled and used as covariates in subsequent analyses.

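### Illicit substance use ends participation, not just stimulation, and the plan does not provide for collecting outcomes afterwards, although the primary analysis is intention-to-treat on all 138

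*Combined protocol and SAP*

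**What the plan says.** **Removal.** Exclusion Criteria, item 1: "Participation will be discontinued if participants use psychoactive illicit substances (except nicotine and alcohol) after study initiation". Detection is frequent. Study Visit Procedures states: "At all visits, individuals will provide a urine screen to detect recent use of drugs of abuse and pregnancy".

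**Analysis set.** Sample Size and the Analytical Plan both state: "Primary data analysis will be done on the Intent to Treat sample (n=138; 69 per Aim: 46 active, 23 sham". Outcome Measure(s) plans a repeated-measures ANOVA of change from baseline for the behavioural outcomes, with AR(1) and other covariance structures considered. No method for missing data is given.

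**Retention.** Sample Size expects 78% retention over the treatment phase, equal attrition in the real and sham groups, and 108 usable data sets at V11. It does not mention protocol-mandated discontinuation.

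**Marijuana.** Item 1 of the Exclusion Criteria sets a 30-day rule, "Any psychoactive illicit substance use (except marijuana, alcohol, and nicotine) within the last 30 days by self-report and urine drug screen", and a separate entry rule, "For marijuana, no use within the last seven days by verbal report and negative (or decreasing) urine THC levels". Its post-entry rule, quoted first above, exempts only nicotine and alcohol. The second eligibility list, in the Study Visit 1 paragraph, asks at item 5 that participants "not currently use psychoactive substances other than alcohol, nicotine, or marijuana".

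**The concern.** Intention-to-treat needs outcomes on everyone randomised, including those who stop the intervention. A rule that ends participation because of what someone does during the trial works against that. Other substance use may change when a person stops smoking or responds to stimulation. Those removed may therefore differ in outcome from those who stay, and a comparison of the remaining data could be biased in a direction that cannot be known beforehand. A repeated-measures model can use visits made before removal, but it cannot recover outcomes that were not collected. Its missing-at-random assumption is also least comfortable when removal follows on-study behaviour.

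The inconsistent marijuana wording adds a practical problem: staff could apply entry or discontinuation differently from one participant to the next.

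**Working it through.** **1. The plan's own figures.** From Sample Size, 138 × 0.78 = 107.64, which reproduces the stated 108. That leaves 138 − 108 = 30 (22%) without usable V11 data. The analysis set also adds up: 2 × (46 + 23) = 138.

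The interval retentions printed beside the 78% multiply to 0.80 × 0.85 = 0.68. That is a separate discrepancy. I use 78% because it is the figure that gives 108.

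**2. Per Aim.** Allocation is "with a 2:1 active versus sham randomization for each Aim". Active: 46 × 0.78 = 35.9, about 36. Sham: 23 × 0.78 = 17.9, about 18.

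**3. Power of a simple comparison.** Two-sample t-test with d = 0.8 and type 1 error 5%. Two-sided testing is my assumption, since the plan does not say. Noncentrality λ = d × √(n₁n₂/(n₁+n₂)), with n₁+n₂−2 degrees of freedom.

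- 46 vs 23 (everyone observed): λ = 0.8 × √(1058/69) = 3.13, power 0.870.
- 36 vs 18 (plan's retention): λ = 0.8 × √(648/54) = 2.77, power 0.776.

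The plan's own calculation uses four time points and an AR(1) correlation that it does not report, so it cannot be reproduced exactly. The figures here ignore any repeated-measures gain.

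**4. Extra loss from the removal rule.** The documents give no rate, so x below is an assumption. It is applied equally to both arms and on top of the 78%: usable N = 138 × 0.78 × (1 − x).

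| Assumed extra loss x | Usable N | Active / sham per Aim | Share of 138 missing | Power |
|---|---|---|---|---|
| 0 | 107.6 | 35.9 / 17.9 | 22.0% | 0.775 |
| 2% | 105.5 | 35.2 / 17.6 | 23.6% | 0.766 |
| 5% | 102.3 | 34.1 / 17.0 | 25.9% | 0.753 |
| 10% | 96.9 | 32.3 / 16.1 | 29.8% | 0.729 |

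Unrounded group sizes are used; 36/18 gives 0.776. If the 78% already contains these removals, the first row applies.

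**5. What is lost, by time of removal.** Table 2 schedules the purchase task and delay discounting at visits 1, 6, 10 and follow-ups, and the cue-reactivity scan at visits 1 and 10. Removal before visit 6 leaves no treatment-phase demand or discounting value after visit 1. Removal before visit 10 leaves no second scan. Craving is scheduled at every treatment visit, so some later craving values would exist.

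**6. Marijuana, side by side.** The 30-day and seven-day entry rules within item 1 of the Exclusion Criteria are tiered and do not contradict each other. The conflict is between lists. Item 1 requires seven days without use and negative or falling THC, and does not exempt marijuana after entry. Item 5 of the second list does not bar current use.

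**The case against.** **The documents do not say that assessments stop.** True. Leaving the study is the natural reading of the rule, but no sentence says that visits or remote EMA end. A reader might infer that outcomes are never collected after removal. What the text supports is that no provision is made for collecting them.

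**The 78% may already include these removals.** Also true. It is an overall rate, taken from published data and prior studies in this population. The documents do not settle whether this loss is extra, so it cannot be called uncounted attrition.

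**The rate may be very small.** Entrants are screened for other illicit use over 30 days and for moderate or severe substance use disorder over about five years. Nothing anchors a high rate, which is why the table starts at zero.

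**Arm-related loss is speculative.** Sample Size expects equal attrition, citing experience with 10 days of TMS, and participants and coordinators are blinded with an active sham. No difference between arms has been shown. Blinding does not prevent on-study behaviour from responding to treatment, however, so informative loss remains possible.

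**Missing data do not by themselves negate intention-to-treat.** Agreed. A likelihood-based fit could keep earlier visits. The lack of a missing-data method applies to every withdrawal, and this rule is one cause among several.

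**Marijuana.** It is tempting to infer that a current user admitted under the second list would be removed at the first positive screen. The documents do not support that. Participants and Procedure applies the criteria described above it at screening, so the seven-day and THC rule would act at entry. The post-entry trigger is use, not a positive screen, and item 1 itself admits falling THC. What stands is a wording conflict, not a demonstrated route to data loss.

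**Conclusion.** The concern holds in limited form. The plan ends participation for illicit psychoactive use after study initiation, exempts nicotine and alcohol, and provides for no outcome collection afterwards, while claiming a primary intention-to-treat analysis of 138. Followed as written, it risks losing outcomes according to behaviour during the trial.

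The possible selectivity of that loss matters more than the lost power. On power, the cost is nil if the 78% includes these removals. Otherwise it is about 1, 2 or 5 percentage points at assumed extra losses of 2%, 5% or 10%, from a base of about 78%. This rests on d = 0.8, a two-sided 5% test, 2:1 allocation, equal loss by arm and a single-time-point t-test. The direction and size of any bias cannot be computed from the documents.

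The marijuana wording is a genuine inconsistency. This review takes no position on which rule is right.

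**What to change.** In item 1 of the Exclusion Criteria, separate discontinuing stimulation from leaving the study. The rule on stimulation remains the sponsor's and need not change.

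Keep discontinued participants who still consent in the scheduled behavioural, CO/cotinine, TLFB and remote EMA assessments, and in the visit 10 MRI where the sponsor's safety rules allow. State in the Analytical Plan that these data enter the intention-to-treat analysis.

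Separately, reconcile the marijuana wording: the seven-day and THC entry rule and the post-entry rule in item 1, against item 5 of the list in the Study Visit 1 paragraph.

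**Cost.** The changes are to protocol wording, and the assessments are already in the schedule. Some visits will be held that would otherwise have been dropped; the documents give no budget from which to price them. Some assessments will also be made under the influence of other substances, which adds noise and should be recorded.
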